## A Introduction

## A1 Study Abstract

Carpometacarpal osteoarthritis (CMC OA) is a prevalent and disabling disease. Trapeziectomy with ligament reconstruction and tendon interposition (LRTI), the most frequently performed procedure for CMC OA, requires prolonged postoperative immobilization which limits patients' abilities to perform ADLs and to work. Trapezium excision and internal brace (IB) stabilization is a largely unstudied novel alternative to LRTI which allows an expedited return to work/activity. In this feasibility and pilot grant application, our overall objective is to investigate critical guestions to inform the planning of a definitive randomized controlled trial (RCT) comparing IB and LRTI for patients with CMC OA. Our central hypothesis is that a prospective RCT comparing LRTI and IB is feasible, and that IB will produce superior patient-reported outcomes to LRTI at 6 weeks and 3 months with an expedited return to work/activity. Our specific aims are to (1) establish feasibility of a definitive trial by determining the randomization rate and followup retention rate, (2) estimate effect sizes and variability in outcomes for planning a definitive RCT, and (3) characterize objective clinical outcomes (thumb range of motion, grip/pinch strength, radiographic outcomes, complications/need for additional surgery) and to identify differences in return to work/activity following IB and LRTI. To achieve our aims, we will randomize 50 patients as they present to the clinics of the 7 Washington University Orthopaedic Hand surgeons to LRTI (control) or IB (experimental). Patients will follow-up at 2 weeks, 4 weeks, 3 months, and 1 year post-operatively. Our primary outcome will be feasibility (randomization rate, follow-up retention rate). Secondary outcomes will be PROMIS and Visual Analog Scale Pain and Satisfaction scores at 6 weeks and 3 months, objective clinical outcomes (thumb range of motion, grip/pinch strength, radiographic outcomes, complications/need for additional surgery), and return to work/activity.

Upon completion of our aims, we expect to demonstrate that a prospective, randomized trial comparing LRTI and IB is feasible, and that patients who undergo IB will have superior short-term patient-reported outcomes to those who undergo LRTI. Furthermore, we will generate effect size and variability estimates for a definitive, subsequent RCT. Should the objectives for this study be successful, we expect to take an important first step in defining the role of the IB procedure in the treatment of CMC OA.

## A2 Primary Hypothesis

Our central hypothesis is that a prospective, randomized trial comparing LRTI and IB is feasible, and that IB will produce superior patient-reported outcomes to LRTI at 6 weeks and 3 months with an expedited return to work/activity.

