Upon successful completion of the proposed research, we expect to (1) demonstrate that randomization into a prospective RCT comparing IB and LRTI is feasible, (2) obtain estimates to inform the sample size and design of a future adequately powered prospective RCT, and (3) show that IB produces superior patient-reported outcomes at 6 weeks and 3 months to LRTI while offering an expedited return to work/activity.

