## C Study Objectives

#### C1 Study Aims and Rationale for Selection of Outcome Measures

Aim 1: Establish feasibility of a definitive trial by determining the proportion of eligible subjects who agree to randomized treatment and determining the followup retention rate. Rationale: To date, no studies have compared IB and LRTI for thumb CMC OA. Our study will assess the feasibility of a prospective RCT comparing outcomes of the two procedures. Hypothesis: A prospective RCT comparing outcomes of IB and LRTI is feasible, as defined by the ability to successfully recruit and randomize  $\geq$ 50 patients over the course of 1 year with a follow-up retention rate of  $\geq$ 90%.

Aim 2: Estimate effect sizes and variability in patient-reported outcomes for planning a definitive, two-arm RCT. Rationale: We will assess patient-reported outcomes (PROMIS UE/physical function, VAS pain, VAS satisfaction) following IB and LRTI. Effect size and variability estimates are required to inform the design of a future definitive trial. Hypothesis: IB will produce superior patient-reported outcomes to those of LRTI at 6 weeks and 3 months.

Aim 3: Characterize objective clinical outcomes (thumb range of motion, grip/pinch strength, radiographic outcomes, and complications/need for additional surgery) and to identify differences in return to work/activity following IB and LRTI at three months. Rationale: Objective clinical outcomes are important predictors of patient function after surgery for thumb CMC OA. IB offers an expedited return to work and activity by allowing patients to forego postoperative casting. Hypothesis: IB will produce similar objective outcomes to LRTI with a quicker return to work/activity.

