## F2 Analysis Plan and Statistical Methods

Patient demographic and clinical characteristics will be summarized using means (standard deviation, SD) or median (25th, 75th) for continuous variables and frequency (percentage) for categorical variables. The recruitment rate (95% confidence interval) will be reported as the number randomized out of the total number of participants approached to participate in the study (screened). Reasons for not wanting to participate will be summarized and reported. The effect sizes and variability of the PROMs for each group will be reported and used to determine the sample size for a larger definitive trial. Differences in PROMs between LRTI and IB at 6 weeks and 3 months will be examined using a two-sample t-test and differences in categorical outcomes (return to work/activity, yes/no, at 3 months) using Pearson chi-squared test. Changes over time will be evaluated graphically to see the trajectory of change over follow-up and for assessing critical time points to inform future study design parameters. Objective parameters will be summarized for each group using descriptive statistics. The significance level will be 0.05 for all tests due to the exploratory nature of the study.

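### Patient-reported superiority sits in the Primary Hypothesis, but it would rest on unadjusted exploratory tests with no rule for which result decides it

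*Combined protocol and SAP*

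**What the plan says.** A2, under the heading Primary Hypothesis, is a compound statement: "Our central hypothesis is that a prospective, randomized trial comparing LRTI and IB is feasible, and that IB will produce superior patient-reported outcomes to LRTI". Its superiority clause, with the timing and the return-to-work part, reads in full "IB will produce superior patient-reported outcomes to LRTI at 6 weeks and 3 months with an expedited return to work/activity". The closing paragraph of A1, and A3, both say the investigators expect to demonstrate better short-term PROMs with the internal brace (IB). The end of B1 lists among the expected results to "show that IB produces superior patient-reported outcomes at 6 weeks and 3 months to LRTI". The Aim 2 hypothesis in C1 repeats the superiority claim, although the aim itself is to estimate effect sizes and variability.

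Other sections rank things differently. A1 states "Our primary outcome will be feasibility (randomization rate, follow-up retention rate") and then "Secondary outcomes will be PROMIS and Visual Analog Scale Pain and Satisfaction scores at 6 weeks and 3 months". F1 sizes the study at 50 from a 12-per-group pilot rule. It gives the main goal as feasibility and planning estimates, and leaves detection of meaningful clinical change to a larger trial.

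C1 names the PROMs as "PROMIS UE/physical function, VAS pain, VAS satisfaction", and E2 confirms that both PROMIS scores are collected. F2 compares them by two-sample t-test at 6 weeks and 3 months, adds a chi-squared test on return to work/activity at 3 months, and says "The significance level will be 0.05 for all tests due to the exploratory nature of the study". D1 and E2 schedule visits at 2 weeks, 4 weeks, 3 months and 1 year. Section 2.d says the study is not blinded.

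**The concern.** Exploratory status is a fair reason to leave tests unadjusted, provided no confirmatory conclusion is drawn from them. Here the same document relies on that status in F2 and, in A1, A2, A3 and B1, expects the tests to establish superiority. It does not say what pattern of results would count. One PROM at one visit, one PROM at both visits, and all PROMs at both visits are each compatible with the text, and their error rates differ greatly.

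What is at stake is the conclusion the trial may draw. The outcomes are self-reported, the trial is open-label and journal publication is planned. One significant score could be presented as confirming a statement headed Primary Hypothesis. In the other direction, a null from about 25 patients per arm could be taken as evidence against IB when the design cannot exclude a moderate benefit.

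**Working it through.** **The plan's own figure.** The only precision figure is in F1: a 95% interval of 0.404 to 0.596 for a 50% randomization rate with n = 100. The Wilson half-width is z√(p(1−p)/n + z²/4n²)/(1 + z²/n) = 1.96 × √(0.0025 + 0.000096)/1.0384 = 0.0962, giving 0.404 to 0.596. It reproduces. No power, effect size or SD is given for any PROM.

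**Inputs.** Total 50 (F1). Two arms with even block sizes (2.d); the ratio is not stated, so 1:1 and 25 per arm are assumed. Retention of 90% (C1, Aim 1) leaves 45. Alpha is 0.05 per test (F2); sidedness is not stated, so two-sided is assumed. Correlations between scores and effects in SD units are assumptions, shown as ranges.

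**Number of PROM tests.** Four scores × 2 times = 8. If the two PROMIS scores count as one, 3 × 2 = 6. If only the scheduled 3-month visit supplies data, 4. The chi-squared test is extra and is not counted below.

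**Chance of at least one false positive.** For k independent tests it is 1 − 0.95^k. For equal correlation ρ it is, to a normal approximation, 1 − ∫φ(u)[Φ((z−u√ρ)/√(1−ρ)) − Φ((−z−u√ρ)/√(1−ρ))]^k du, with z = 1.96. Simulated t-tests with 25 per arm agree to within about half a percentage point.

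| PROM tests | Independent | ρ = 0.5 | ρ = 0.7 |
|---|---|---|---|
| 8 | 1 − 0.95⁸ = 33.7% | 25% | 19% |
| 6 | 1 − 0.95⁶ = 26.5% | 21% | 16% |
| 4 (3 months only) | 1 − 0.95⁴ = 18.5% | 16% | 13% |

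Counting only false positives in IB's favour, eight tests give 1 − 0.975⁸ = 18.3% if independent, and about 13% and 9.5% at ρ = 0.5 and 0.7.

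**How much the missing rule matters.** Simulation, eight tests, 25 per arm, results in IB's favour:

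| Rule | ρ | False positive | Power if every effect is 0.5 SD |
|---|---|---|---|
| Any of 8 | 0.5 | 12.7% | 83% |
| All 8 | 0.5 | 0.02% | 6% |
| Any of 8 | 0.7 | 9.5% | 74% |
| All 8 | 0.7 | 0.1% | 13% |

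**What a null would say.** The half-width for a difference in SD units is t × √(1/n₁ + 1/n₂). With 25 and 25: 2.011 × 0.2828 = 0.57 SD. With 22 and 23: 2.017 × 0.2982 = 0.60 SD. An estimate near zero would leave a 0.5 SD benefit inside the interval.

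**Power of one test** (noncentral t, 25 per arm, noncentrality d√12.5): 18% at 0.3 SD, 41% at 0.5 SD, 79% at 0.8 SD. With 45 evaluable patients, power at 0.5 SD is 37%.

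**Timing.** The analysis is at 6 weeks and 3 months; the visits are at 2 and 4 weeks, 3 months and 1 year. Half of the eight tests have no scheduled assessment behind them.

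**The case against.** The strongest reply is that this is a pilot and largely says so. Feasibility is the other half of the A2 hypothesis and the declared primary outcome, the PROMs are secondary, and F2 labels the tests exploratory. Unadjusted 0.05 is defensible on those terms. Low power for secondary outcomes comes with a 12-per-group rule, and the plan claims no PROM power. B1 states an expectation rather than a decision rule. All of this stands, and it rules out several stronger readings.

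A reader might infer that the plan names no PROM or time point. It names both; what is missing is a single deciding one, or an any-or-all rule. A reader might infer that any one p < 0.05 would be declared success. No section says so, and requiring both times in A2 is an equally natural reading. A reader might infer that no result could be informative. That goes too far: consistent benefit on all scales would not be a multiplicity artefact, with a false-positive rate below 0.3% for all eight at the correlations simulated (up to 0.8). The 0.5 SD effect is also an assumption, and at 0.8 SD a single test has 79% power.

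The reply does not remove the conflict itself. The superiority wording recurs in A1, A2, A3, B1 and Aim 2, and nothing in F2 says that the tests will not be used to conclude it.

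**Conclusion.** The concern holds as a conflict between the stated conclusions and the analysis that would support them; the choice of test and the sample size are not at fault. The plan cannot both waive error control as exploratory and expect to show superiority without saying which result decides. An isolated significant PROM would be weak support: the any-positive rate under no difference is 34%, 25% and 19% for eight tests at correlations 0, 0.5 and 0.7, and 19%, 16% and 13% if only the four 3-month tests can be run. A null with an estimate near zero would not exclude a 0.5 SD benefit, given half-widths of 0.57 to 0.60 SD.

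These figures assume 1:1 allocation, two-sided tests and equal correlation between scores. The count of eight also assumes that the two PROMIS scores are tested separately and that 6-week data exist. The point deserves correction because it governs what the trial may conclude, and the correction is cheap.

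**What to change.** - In A1, A2, A3, the end of B1 and the Aim 2 hypothesis in C1, limit the trial's conclusions to feasibility plus estimation, and label PROM superiority an exploratory secondary hypothesis. All five places need the edit, or the conflict remains.
- In F2, report each PROM contrast as a mean difference with its 95% CI, and state that no superiority conclusion will be drawn from the tests.
- Optionally, if one test is kept, name in advance one PROM at a scheduled visit, for example PROMIS Upper Extremity at 3 months, and call the rest supportive. This settles which result decides but leaves power at about 41% for an assumed 0.5 SD effect.
- Reconcile the 6-week analysis time with the visit schedule, which has no 6-week visit.

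The edits to wording need no extra patients. The 6-week item may affect the schedule, depending on how it is reconciled. The cost is that fewer results may be called significant.

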## A3 Purpose of the Study Protocol

The purpose of our study protocol is to investigate critical questions to inform the planning of a definitive randomized controlled trial (RCT) comparing IB and LRTI for

patients with CMC OA. We expect to demonstrate that a prospective, randomized trial comparing LRTI and IB is feasible, and that patients who undergo IB will have superior short-term patient-reported outcomes to those who undergo LRTI. Furthermore, we will generate effect size and variability estimates for a definitive, subsequent RCT. Should the objectives for this study be successful, we expect to take an important first step in defining the role of the IB procedure in the treatment of CMC OA.

## **B** Background

#### B1 Prior Literature and Studies and Rationale for this Study

Thumb carpometacarpal osteoarthritis (CMC OA) is a common disease, affecting up to 25% of women and 8% of men, and is increasing in prevalence with the aging population. When symptomatic, loss of thumb function can impart up to 50% impairment to the upper extremity. Nonoperative treatments for thumb CMC OA include activity modification, splinting, anti-inflammatory medications, and intra-articular corticosteroid injections. When nonoperative treatments fail, surgery may be considered.

Surgeries for advanced thumb CMC OA all incorporate trapezium excision to eliminate painful bony contact. The majority of hand surgeons in the United States supplement trapeziectomy with suspension using the FCR tendon (Figure **1)**. This suspensionplasty is touted to reduce subsidence of the thumb metacarpal and improve pinch strength over simple trapeziectomy. However, LRTI using the FCR tendon increases surgical time, increases perioperative complications, and increases costs of surgery. Postoperatively, patients are typically placed in rigid immobilization for 4-6 weeks and require 3 months of healing prior to strengthening. Despite both the popularity and heightened direct/indirect costs, comparative studies have not demonstrated any long term benefit of LRTI over simple trapeziectomy and hematoma arthroplasty. Gangopadhyay et al randomized 174 thumbs to trapeziectomy alone, LRTI, or trapeziectomy and palmaris longus interposition. Of the 153 thumbs with ≥5 years follow-up, 78% had good results and pain relief was durable, and there were no differences in pain, function (grip/pinch strength), or complications among the three groups. In their 2015 Cochrane Review, Wajon et al demonstrated no benefit to pain or function from LRTI compared to simple trapeziectomy, although they acknowledged that the evidence was of low quality.

**Figure 1**: Steps in trapeziectomy with LRTI. **A**: Trapeziectomy. **B**: Reconstruction performed with a LRTI using FCR tendon. Radial half of FCR tendon passed through a tunnel in base of first metacarpal. **C**: Tendon sutured to itself as a space-filling arthroplasty, augmented by Kirschner wire to prevent subsidence.

Hand surgeons, however, continue to perform LRTI secondary to the desire to provide mechanical support for the thumb metacarpal and to avoid the exposed Kirschner wires (K-wires) associated with simple trapeziectomy. Recently, techniques have been described that provide immediate internal suspension of the thumb metacarpal after trapeziectomy without requiring prolonged immobilization or painful K-wires. Internal brace (IB, **Figure 2)**, a technology used in ligament augmentation in lateral ankle instability, syndesmosis injuries, and scapholunate ligament reconstruction , has been used at our institution for thumb CMC OA with encouraging outcomes in the short-term (unpublished data). The IB procedure allows the patient to forego postoperative casting or K-wire pinning and return to all activities at 6 weeks.

**Figure 2**: Illustration of internal brace procedure. Trapeziectomy is performed in standard fashion. Longitudinal traction is applied to the thumb. A suture anchor with suture tape is inserted into a drill hole at the radial aspect of the thumb metacarpal base. A second suture anchor is inserted into a drill hole at the radial base of the index metacarpal such that the suture tape suspends the thumb at the natural groove. Thumb position and tension are then assessed.

To date, the literature lacks high level clinical evidence to define IB's role in the treatment of thumb CMC OA. A prospective, randomized controlled trial (RCT) is required to compare the procedure's effectiveness in relieving pain and restoring function against that of LRTI. Therefore, we propose a pilot RCT comparing patient-reported outcomes following IB and LRTI to establish feasibility and generate effect size and variability estimates for a definitive, subsequent RCT (Aims 1 & 2). Recognizing that objective clinical measures such as thumb range of motion, grip/pinch strength, radiographic outcomes, and complications/need for additional surgery are critical in measuring IB's effectiveness against LRTI, we will characterize the two procedures with respect to these parameters along with return to work/activity (Aim 3).

Upon successful completion of the proposed research, we expect to (1) demonstrate that randomization into a prospective RCT comparing IB and LRTI is feasible, (2) obtain estimates to inform the sample size and design of a future adequately powered prospective RCT, and (3) show that IB produces superior patient-reported outcomes at 6 weeks and 3 months to LRTI while offering an expedited return to work/activity.

## C Study Objectives

#### C1 Study Aims and Rationale for Selection of Outcome Measures

Aim 1: Establish feasibility of a definitive trial by determining the proportion of eligible subjects who agree to randomized treatment and determining the followup retention rate. Rationale: To date, no studies have compared IB and LRTI for thumb CMC OA. Our study will assess the feasibility of a prospective RCT comparing outcomes of the two procedures. Hypothesis: A prospective RCT comparing outcomes of IB and LRTI is feasible, as defined by the ability to successfully recruit and randomize  $\geq$ 50 patients over the course of 1 year with a follow-up retention rate of  $\geq$ 90%.

Aim 2: Estimate effect sizes and variability in patient-reported outcomes for planning a definitive, two-arm RCT. Rationale: We will assess patient-reported outcomes (PROMIS UE/physical function, VAS pain, VAS satisfaction) following IB and LRTI. Effect size and variability estimates are required to inform the design of a future definitive trial. Hypothesis: IB will produce superior patient-reported outcomes to those of LRTI at 6 weeks and 3 months.

Aim 3: Characterize objective clinical outcomes (thumb range of motion, grip/pinch strength, radiographic outcomes, and complications/need for additional surgery) and to identify differences in return to work/activity following IB and LRTI at three months. Rationale: Objective clinical outcomes are important predictors of patient function after surgery for thumb CMC OA. IB offers an expedited return to work and activity by allowing patients to forego postoperative casting. Hypothesis: IB will produce similar objective outcomes to LRTI with a quicker return to work/activity.

## D Study Design

#### D1 Overview or Design Summary

Our study has been registered on ClinicalTrials.gov. All facets of our study design, analysis, and interpretation will adhere to Consolidated Standards of Reporting Trials (CONSORT) guidelines. Data will be managed using REDCap (Research Electronic Data Capture) electronic data capture tools hosted at our institution. REDCap is a secure, web-based application designed to support data capture for research studies, providing: 1) an intuitive interface for validated data entry; 2) audit trails for tracking data manipulation and export procedures; 3) automated export procedures for seamless data downloads to common statistical packages; and 4) procedures for importing data from external sources.

The research team will identify potential participants as they present to the clinics of one of our seven Orthopaedic Hand and Upper Extremity surgeons. The study population will consist of patients aged 50 years and older who are English-speaking and community-dwelling. These patients will have a confirmed diagnosis of isolated thumb CMC arthritis. Patients will not have carpal tunnel syndrome (to avoid outcome data confusion), rheumatoid/inflammatory arthritis, or a history of chronic opioid use. The research team will block randomize the participants into a control group (LRTI) and a comparison group (IB); block sizes will be 4, 6, and 8.

#### Study Aim 1

The team will review patients' medical records and radiographs to determine potential participants' eligibility. The team will recruit eligible individuals during their clinic appointments using an information form outlining the benefits and relative limitations of each procedure. Patients who are interested in participating in the study will undergo initial testing at their clinic appointment, at which time they can also provide informed consent. Feasibility will be recorded by means of randomization rate and follow-up retention rate throughout the enrollment process. In the event that a patient declines randomization into our study, we will record the patient's reason for declining.

Following the consent process, the study will proceed as follows:

- 1. Patient will undergo the surgery to which they are randomized, either LRTI or IB, performed by one of the seven Washington University orthopaedic hand surgeons.
- 2. All patients will follow-up in clinic 2 weeks, 4 weeks, 3 months, and 1 year postoperatively.

Patients will undergo a standardized postoperative recovery and therapy regimen:

#### Study Aims 2 & 3

PROMIS Physical Function and Upper Extremity scores will be collected at all clinic visits on iPad as per standard protocol for all patients presenting to a Washington Orthopaedic Surgery clinic. Thumb Universitv ROM at carpometacarpal. metacarpophalangeal, and interphalangeal joints will be collected by a member of our team at 4 weeks, 3 months, and 1 year after surgery. Visual Analog Scale Pain and Satisfaction scores will be collected by a member of our team at 2 weeks, 4 weeks, 3 months, and 1 year post-op. Grip and pinch strength (3-point and lateral vs contralateral values and vs preoperative values) will be collected at pre-op visit and all post-op visits except the 2 week visit. Radiographic subsidence will be measured via C-arm radiographs at 3 months and 1 year post-op. Complications (mild, moderate, severe) will be recorded throughout the course of the study at all time points. Mild complications will be defined as those with minor clinical impact (i.e., scar tenderness or sensory disturbances). Moderate complications will be defined as clinically relevant with delay in patient recovery, but not severe enough to necessitate revision surgery and resolve by 12 months after surgery (i.e., mild CRPS type I, tendinitis, neuromas treated with steroid injections). Severe complications will be defined as those which result in revision surgery, pain at rest, or impaired hand function at 12 month exam (i.e., severe CRPS) type I or tendinitis and neuromas that do not improve with corticosteroid injections and require surgery). We will document patient return to work/activity at each follow-up appointment.

